The study team may enrol additional participants to within 10% of the planned 100.

Note: "Enrolled" means a participant's, or their legally acceptable representative's, agreement to participate in a clinical study following completion of the informed consent process and after study personnel have confirmed that all eligibility criteria have been met. Potential participants who are screened for the purpose of determining eligibility for the study, but do not participate in the study, are not considered enrolled, unless otherwise specified by the protocol.

Intervention Arms and Duration:

The total duration of the study, including screening, treatment, and post-treatment follow-up, is not expected to exceed 79 weeks for each participant:

- Arm 1: 24 weeks GSK3228836 + 24 weeks PegIFN + 24 weeks off-treatment
- Arm 2: 12 weeks GSK3228836 + 24 weeks PegIFN + 36 weeks off-treatment

[figure not shown]
A 45-day screening window is included in the total study duration. Eligible participants who fall outside of the 45-day window may be re-screened at the discretion of the Investigator/site.

There are no plans for group dose adjustments. Individual dose adjustments for GSK3228836 for safety are outlined in the monitoring/stopping criteria. Individual dose adjustments for PegIFN for safety are outlined in the monitoring/stopping criteria and are permitted down to 90 mcg/mL.

Participants that leave the study early will not be replaced.

Data Monitoring/ Other Committee: Yes

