4. STUDY DESIGN

4.1. Overall Design

This is a Phase IIb, multi-centre, randomised, open-label study to assess the efficacy and safety of sequential treatment with GSK3228836 (300 mg/week for 12 or 24 weeks) followed by PegIFN (180 mcg/week for up to 24 weeks) in participants with CHB on stable NA therapy. During the GSK3228836 treatment period, a 300 mg loading dose will be administered on Day 4 and Day 11. Participants will continue their NA therapy for the duration of the study.

Participants will be randomised (1:1) into one of two parallel treatment arms.

1. 300 mg GSK3228836 once/week for 24 weeks (plus loading dose on Day 4 and 11) followed by PegIFN (180 mcg/week for up to 24 weeks). Participants will be followed up for an additional 24 weeks (off-treatment phase) once PegIFN treatment is complete.

2. 300 mg GSK3228836 once/week for 12 weeks (plus loading dose on Day 4 and 11) followed by PegIFN (180 mcg/week for up to 24 weeks). Participants will be followed up for an additional 36 weeks (off-treatment phase) once PegIFN treatment is complete.

The planned duration of GSK3228836 is 24 weeks and 12 weeks in Treatment Arm 1 and 2 respectively. If a participant prematurely discontinues GSK3228836 treatment the participant is encouraged to complete the SoA as per the planned GSK3228836 dosing period. At the end of the planned GSK3228836 dosing period, participants will be re-assessed for eligibility to start PegIFN treatment based on the label.

1. Participants immediately eligible for PegIFN will begin treatment
2. Participants who are not considered eligible will be re-assessed for eligibility and may delay start of PegIFN treatment for up to 12 weeks.
3. Participants who fail to meet PegIFN eligibility criteria by PegIFN Eligibility Week 13 (i.e. can no longer receive at least 12 weeks of PegIFN treatment) will not receive treatment with PegIFN.

Note: all participants are expected to end PegIFN treatment at the same time, regardless of when they start therapy (Treatment Group 1: all participants should complete treatment by Week 48; Treatment Group 2: Week 36).

As such, the planned treatment duration with PegIFN for participants on study 209348 may vary from a minimum of 12 weeks to a maximum of 24 weeks.

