4.1.3. Relapse Definition

One way to illustrate response durability and the benefit of adding PegIFN sequential therapy is to consider time to relapse among Bepi and/or PegIFN End of Treatment (EOT) responders. Time to relapse from end of Bepi treatment will be calculated using the Bepirovirsen EOT window with the following limits referred to in Section 4.2.2.1.

Only participants who were virologic responders at the end of Bepirovirsen EOT (See Section 4.2.2.1 windowing rules) without any prior rescue medication will be considered.

The start date used to measure the time to relapse will be the date of the first visit in the appropriate window where the participant is a responder and remains a responder at all subsequent visits within the window. Response and relapse rates can be evaluated under the conservative and modified definition of SVR.

Discontinuation interruption in, or non-adherence to GSK3228836 and PegIFN related or unrelated to wide disruptive events (WDEs) will be analysed as collected when determining relapse (treatment policy strategy).

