4.1.3.1. Relapse under Conservative Definition (SVR)

Relapse date is defined as the first visit after the appropriate window end date where observed data for either HBsAg or HBV DNA is greater than the lower limit of quantification (LLOQ) or the use of rescue medication.

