- Categorical changes from baseline in HBsAg (e.g., <0.5, ≥0.5, ≥1, ≥1.5, ≥3 log₁₀ IU/mL) and in HBV DNA (e.g., <1, ≥1, ≥2, ≥3 log₁₀ IU/mL). Change from baseline will be presented at each visit and for the following time periods: up to and including Week 6, up to and including Week 12, up to and including Week 24, up to and including off-treatment Week 24. Data will be presented overall and by the baseline stratification factors defined in [Table 1](#). Data will be summarized using planned visits.
- ALT normalisation (ALT ≤ ULN) over time in absence of rescue medication in participants with baseline ALT > ULN.
- HBe antibody (anti-HBeAg) levels.

Population Summary: Percentage of participants in each category for each treatment arm.

Continuous Variables

Continuous variables for the secondary objective are defined as follows:

- Actual values and change from baseline over time of HBsAg, HBV DNA, and HBeAg levels (only in HBeAg Positive Participants at baseline).
- Actual values and change from baseline over time for HBs antibody (anti- HBsAg) levels.
- Actual values and change from baseline over time for ALT.

Population Summary: Mean values and mean changes from baseline of each variable for participants in each treatment arm.

Time to Event Variables:

A time to event variable for this objective is defined as:

- Time to ALT normalisation in absence of rescue medication in participants with baseline ALT>ULN.

Population Summary: Turnbull's estimator for nonparametric estimation of Time to ALT normalisation in each treatment arm.

ALT normalization is defined in participants with ALT>ULN at baseline as a return to <ULN (ULN = 40 for males and 33 in females). Time to ALT normalization is defined as time from baseline to the first follow-up where subject's ALT has returned to normal.

For participants who withdraw from the study or Participants with ALT>ULN at the end of study (EoS), time to ALT normalization will be censored after the time of the last visit with non-missing ALT value available. Participants who receive rescue medication cannot go on to achieve the event of 'ALT normalization in the absence of rescue medication'; such participants will be censored at the end of the follow up period.

In order to determine if the addition of a PegIFN treatment after completing 12 or 24-weeks of Bepirovirsen delays relapse, an additional time to event variable is defined as follows:

- Time from Bepi EOT to Relapse by HBsAg Categories

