Population summary: summary statistics of the time from Bepirovirsen end of treatment to relapse including: N(%) with relapse, mean, standard deviation, median, minimum, and maximum using the number of participants achieving VR at Bepi EOT. Additionally, a Kaplan-Meier plot and associated percentiles will be produced to provide a graphical comparison of time to relapse between treatment arms.

Only participants who were virologic responders at the end of Bepirovirsen treatment will be considered, since they are the only ones who can relapse. Time to relapse is defined as the first time point where the participant can no longer be considered a responder by the primary estimand for the conservative definition. This includes observed elevation(s) in either HBsAg or HBV DNA or rescue medication usage. Generally, time from end of Bepirovirsen treatment to relapse will be calculated from the date of the planned Week 24 or 12 visit (for arms 1 and 2 respectively), where HBsAg<LLOQ and HBV DNA<LLOQ,

until the first visit after the planned Week 24 or 12 visit where HBsAg \geq LLOQ or HBV DNA \geq LLOQ.

4.3.1.2. Durability of Virological Response after Sequential Therapy with 12 Weeks of GSK3228836 Followed by up to 24 Weeks of PegIFN

The estimand strategy supporting this secondary objective is the same strategy defined in Section 4.3.1.1 and focuses on the timepoints following the 24 weeks off-treatment period(i.e., Week 30 and Week 36).

4.3.1.3. Comparison of Efficacy Between Treatment Arms of 12 and 24 Weeks of GSK3228836 Followed by up to 24 Weeks of PegIFN

The estimand strategy for this objective are defined as follows:

- **Population:** Participants with CHB on stable NA therapy, regardless of discontinuation of, interruptions in or adherence to GSK3228836 or PegIFN, had they not been affected by wide disruptive events.
- **Treatment:** 300 mg GSK3228836 for 12 or 24 weeks followed by up to 24 weeks of PegIFN therapy while on stable NA therapy. One treatment comparison between Arms 1 and 2 up to 24 weeks off treatment.

- **Intercurrent Events:**
 - Discontinuation of, interruption in, and non-adherence to GSK3228836 and PegIFN will be analysed as collected (treatment policy).
 - PegIFN ineligibility will be analysed as collected (treatment policy)
 - Participants who have used rescue medication will be incorporated in the definition of the endpoint (composite strategy)

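### The time-to-relapse analysis is meant to show whether adding PegIFN delays relapse, but both arms receive PegIFN, and its follow-up horizon and censoring rule are not fixed

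*SAP*

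**What the plan says.** SAP 4.3.1.1 gives the purpose of the variable as "In order to determine if the addition of a PegIFN treatment after completing 12 or 24-weeks of Bepirovirsen delays relapse". SAP 4.1.3 gives the same motive: "One way to illustrate response durability and the benefit of adding PegIFN sequential therapy is to consider time to relapse".

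The design has no PegIFN-free arm. Protocol 4.1 says "Participants will be randomised (1:1) into one of two parallel treatment arms", and both arms go on to PegIFN for up to 24 weeks. The synopsis gives "Arm 1: 24 weeks GSK3228836 + 24 weeks PegIFN + 24 weeks off-treatment" for the first; Arm 2 is 12 weeks of GSK3228836, 24 of PegIFN and 36 off treatment.

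Among responders at the end of bepirovirsen, SAP 4.3.1.1 plans "summary statistics of the time from Bepirovirsen end of treatment to relapse including: N(%) with relapse, mean, standard deviation, median, minimum, and maximum". It also plans a Kaplan-Meier plot with percentiles, "to provide a graphical comparison of time to relapse between treatment arms".

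Relapse is defined in more than one place:
- SAP 4.1.3: "The start date used to measure the time to relapse will be the date of the first visit in the appropriate window" at which the participant is a responder and stays one for the rest of the window.
- SAP 4.1.3.1: relapse is the first visit after the window end date at which HBsAg or HBV DNA "is greater than the lower limit of quantification (LLOQ) or the use of rescue medication".
- SAP 4.3.1.1: relapse is the point at which the participant stops being a responder under the primary estimand. As a general rule, time runs from the planned Week 24 or Week 12 visit to the first later visit at or above LLOQ.

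**The concern.** There are two problems. First, a contrast between two PegIFN-containing arms carries no information on the effect of adding PegIFN, whatever the estimator. A reader who takes the stated purpose at face value would credit or discount PegIFN on the strength of a difference in bepirovirsen duration.

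Second, bepirovirsen ends 12 weeks earlier in Arm 2 while the last visit is at Week 72 in both arms. A crude percentage and a crude mean both depend on how long people are watched. If the extra Arm 2 visits count, these summaries can differ between arms with no true difference in relapse.

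**Working it through.** **1. The plan's own time points.** SAP 4.1 puts the end of 24 weeks off treatment at Week 72 (Arm 1) and Week 60 (Arm 2), and the end of study at Week 72 in both arms. The schedule reproduces these: 24+24+24 = 72; 12+24+24 = 60; 12+24+36 = 72.

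**2. Follow-up from the end of bepirovirsen.** Target days are from SAP 4.2.2.1 (Tables 2 and 3) and 6.2.8 (Table 19).
- Arm 1 to the last visit: 498 − 162 = 336 days = 48 weeks.
- Arm 2 to the last visit (off-treatment Week 36): 498 − 78 = 420 days = 60 weeks.
- Arm 2 to off-treatment Week 24: 414 − 78 = 336 days = 48 weeks.

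The horizon is thus 48 weeks in both arms if relapse stops where the primary estimand stops, and 48 against 60 if the rule is open-ended. Off-treatment Weeks 30 and 36 collect HBsAg and HBV DNA in Arm 2 only (Protocol Table 7).

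**3. Crude percentage relapsed under the open-ended rule, with the same relapse distribution in both arms.** Let p be the proportion relapsed by week 48 (Arm 1). The documents give no relapse rate, so p from 20% to 80% is an assumption. Arm 2 then shows:
- constant hazard: 1 − (1−p)^(60/48);
- declining hazard (Weibull, shape 0.5): 1 − (1−p)^√(60/48);
- no relapse until week 24, when planned PegIFN ends, then constant hazard: 1 − (1−p)^(36/24).

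| Arm 1, 48 wk | Arm 2, constant | Arm 2, declining | Arm 2, from week 24 only |
|---|---|---|---|
| 20% | 24.3% | 22.1% | 28.4% |
| 30% | 36.0% | 32.9% | 41.4% |
| 50% | 58.0% | 53.9% | 64.6% |
| 70% | 77.8% | 74.0% | 83.6% |
| 80% | 86.6% | 83.5% | 91.1% |

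The gap runs from 2.1 points (20%, declining) to 14.6 points (50%, from week 24 only). It is zero if nobody relapses after week 48.

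**4. Crude mean time, constant hazard, p = 50%.** The rate is λ = ln 2/48, so 1/λ = 69.25 weeks. With F(T) the proportion relapsed by T, the mean among relapsers is 1/λ − T(1−F)/F.
- Arm 1: 69.25 − 48 × 0.5/0.5 = 21.2 weeks.
- Arm 2: 69.25 − 60 × 0.420/0.580 = 25.7 weeks.

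If non-relapsers enter at their last visit, the mean is F(T)/λ: 34.6 against 40.1 weeks. Either way Arm 2 looks better on the mean while looking worse on the percentage.

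**5. After the fix.** With both arms cut at 48 weeks, identical relapse distributions give identical percentages and means. Kaplan-Meier read at 48 weeks also agrees, provided non-relapsers are censored. SAP 4.3.1.1 states a censoring rule for ALT normalisation but none for relapse.

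**6. The definitions side by side.**
- Start: the window opens on day 148 (Arm 1) or 64 (Arm 2), so the SAP 4.1.3 start can precede the planned visit by up to 162 − 148 = 78 − 64 = 14 days.
- Earliest relapse: after the window end in SAP 4.1.3.1, after the planned visit in 4.3.1.1. The window can close up to 182 − 162 = 98 − 78 = 20 days after target.
- Threshold: above LLOQ in 4.1.3.1, both forms in 4.1.3.2, at or above LLOQ in 4.3.1.1. SAP 4.2.2.2 makes a value at LLOQ an SVR non-response, so that participant fails SVR but has not relapsed under 4.1.3.1.

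**The case against.** The strongest reply is that the SAP attaches its between-arm comparison to the Kaplan-Meier output, not to the crude statistics, and that Kaplan-Meier copes with unequal follow-up. This stands, subject to the missing censoring rule. A reader of the summary list alone might infer that relapse is reported only crudely; the documents do not support that.

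A reader might also infer that the analysis is biased against the 12-week regimen and could distort the Phase III choice. That goes too far. The percentage tilts against Arm 2 but the mean tilts towards it, and under the primary-estimand sentence there is no imbalance at all. Regimen selection rests on the SVR comparison in SAP 4.3.1.3, which uses 24 weeks off treatment in both arms and supplies posterior probabilities for that purpose. Nothing in the SAP uses crude relapse to choose a regimen; the internal decision framework is in a charter that is not available here.

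The threshold mismatch affects only values exactly at LLOQ, and the 4.3.1.1 start date is offered as a general rule, so 4.1.3 may be meant as the detailed one. These are reconciliation points of small size.

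On the comparator, Protocol 2.1 names study 209668 as the source of response without PegIFN. The SAP uses it only for a conditional difference in SVR rates (4.2.2), not for relapse. Kaplan-Meier does nothing to fill that gap.

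**Conclusion.** The analysis as written cannot determine whether adding PegIFN delays relapse. This follows from the design and needs no assumption.

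The horizon is internally inconsistent: 48 weeks in both arms on one reading, 48 against 60 on the other. On the second reading the crude percentage is inflated in Arm 2 by about 2 to 15 points, and the crude mean is lengthened in Arm 2, when true relapse is identical. The sizes rest on assumed relapse of 20% to 80% by week 48 and three assumed hazard shapes. The directions need only that some relapses occur after week 48.

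Severity is minor to moderate: the endpoint is descriptive, no hypothesis is tested, and a Kaplan-Meier display is already planned.

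**What to change.** - **Aim.** In SAP 4.1.3 and 4.3.1.1, restate the purpose as describing durability of response by arm. Draw a PegIFN conclusion only from a specified comparison with the bepirovirsen-alone data of study 209668 under the same relapse definition, at matching duration if such an arm exists. The documents do not show that one does for each duration.
- **Horizon.** State 48 weeks after the end of bepirovirsen for the between-arm N(%).
- **Estimator.** Replace the crude mean with Kaplan-Meier relapse-free estimates and intervals at common times up to 48 weeks, censoring non-relapsers at their last assessment.
- **Definitions.** Reconcile SAP 4.1.3 to 4.1.3.2 with 4.3.1.1 on start date, earliest countable relapse and threshold. Use at or above LLOQ throughout, to match the SVR definition.

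The cost is SAP wording and one revised table. Arm 2 data after 48 weeks leave the between-arm summary but remain in the Week 30 and 36 durability analysis of SAP 4.3.1.2.

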4.3.1.4. Sensitivity Analyses

For the estimand supporting the objective of comparing efficacy between treatment arms, a sensitivity analysis will be performed using the Bayesian model described in Section 4.2.2 assuming missing at random whereby a participant's response will be imputed using all available data (on- and off-treatment values) for participants who completed the study.

4.3.1.5. Other Secondary Endpoints

Other than the HBsAg and HBV DNA data supporting the secondary objective of comparing efficacy between treatment arms, missing data for variables defined in any other secondary or exploratory estimand will be analysed as collected, assuming missing completely at random.

4.4. Exploratory Endpoint Analyses

CCI

[figure not shown]

CCI

CCI

4.4.2. Pharmacokinetic (PK) Analyses

Pharmacokinetic analyses will be based on the PopPK analysis instead of the pharmacokinetic population, as no intensive PK was collected.

Controlled early access to unblinded PK and PKPD related data will be granted to the designated representative(s) to perform the population PK and PKPD dataset preparation, model development and any PK review necessary for planned or unplanned safety reviews.

4.4.2.1. PK Endpoints / Variables

PK of GSK3228836 and PegIFN will be characterised. In all participants, GSK3228836 and PegIFN concentration at the end of dosing interval (C_{τ}) and terminal half-life ($t_{1/2}$) will be estimated, as data permits.

PK parameters will be calculated by standard non-compartmental analysis using the currently supported version of WinNonlin. All calculations of non-compartmental parameters will be based on actual sampling times. PK parameters listed will be determined from the plasma concentration-time data, as data permits.

Table 6 PK Parameters and Parameter Description

Parameter	Data	Analyte	Parameter Description
C_{τ}	All Participants	GSK3228836 PegIFN	Concentration at the end of the dosing interval.
$t_{1/2}$	All Participants	GSK3228836 PegIFN	Terminal half-life determined using concentrations collected during the off-treatment period.

C_{τ} = concentration at the end of dosing interval; $t_{1/2}$ = terminal half-life.

4.4.2.2. Statistical Analyses / Methods

Unless otherwise specified, endpoints/variables defined in [Table 6](#) will be summarised using descriptive statistics, graphically presented (where appropriate) and listed. Descriptive statistics for continuous variables will summarise n, arithmetic mean, SD, 95% CI, median, minimum, maximum, geometric mean with associated 95% CI, and the between-participant CV (%CV_b) for the geometric mean.

PK parameters (C_{τ} and $t_{1/2}$) of GSK3228836 and PegIFN will be summarised and listed by treatment arm, IP, and study visit (only applies to C_{τ}). PK C_{τ} -time plots will be created and compared by the same factors.

4.4.2.3. PK-PD Endpoints / Variables

PK-PD relationships including PK-efficacy relationships and PK-safety relationships will be evaluated using the pre-specified interim and end of study data, as data permits.

To evaluate PK-efficacy relationship and PK-safety relationship, exploratory graphical analyses will be initially performed for efficacy and safety endpoints. If a relationship between exposure and efficacy and/or safety endpoints is present, population PK-PD modelling may be conducted using nonlinear mixed effect methods. Data from this study may be combined with other studies for population PK/PD modelling.

Full details of PK-PD and Population PK analysis will be described in a separate analysis plan developed by CPMS. Results of the PK-PD analyses will be summarized in a separate report.

Efficacy Assessments

Efficacy assessments for PK-PD relationship may include but are not limited to, as data permits:

- **Categorical:** virologic response, seroclearance (HBsAg <LLOQ, HBV DNA <LLOQ), and seroconversion (anti-HBsAg and anti-HBeAg).
- **Change from Baseline:** HBsAg, HBV DNA, anti-HBsAg and anti-HBeAg levels.
- **Time to Event:** virologic response (HBsAg and HBV DNA levels < LLOQ), nadir of HBsAg and HBV DNA, HBsAg <LLOQ, HBV DNA <LLOQ, seroconversion (anti-HBsAg and anti-HBeAg), peak of ALT flares.

Safety Assessments

Safety assessments for PK-PD relationship include but are not limited to vital signs, laboratory measurements and AEs.

PK Assessments

PK assessments include but are not limited to C_{τ} and terminal half-life ($t_{1/2}$). Data from this study may be combined with other studies for population PK modelling.

4.4.3. Safety and Tolerability

The safety profile of sequential therapy with GSK3228836 (up to 24 weeks) followed by PegIFN (up to 24 weeks) in participants with CHB on stable NA therapy will be investigated.

Clinical assessments for safety and tolerability evaluation include laboratory measurements and AEs at timepoints specified in the SoA.

4.4.4. Pharmacodynamic Effect of GSK3228836 and PegIFN Sequential Therapy on Exploratory Biomarkers

The pharmacodynamic effect of GSK3228836 and PegIFN sequential therapy will be assessed on the exploratory viral biomarkers HBV core related antigen (HBcrAg) and HBV RNA at timepoints specified in the SoA. Details will be described in a separate PK-PD analysis plan developed by CPMS.

CCI

CCI

CCI

